10.5. Analysis of safety data

Adverse events will be listed and/or summarized. Device deficiencies and concomitant medications will be listed.

10.6. Sample size

Input for the sample size calculations i.e., means and standard deviations are based on three exploratory studies CP322, CP323 and CP324. The studies investigated earlier prototypes of the micro-hole catheter with identical or similar endpoints in populations of both IC users and healthy volunteers.

A sample size for the primary endpoint of residual urine at 1st flow stop (RV1) is judged to be accommodated by 60 subjects with a power of ~ 90%, assuming a difference of 15 mL, a sdcomparator of 50 mL and a sdactive of 15 mL (please see Table 10-1).

Table 10-1 Sample size calculation of Residual urine at 1st flow stop in a cross-over design, solving for varying power and number of subjects, assuming no within subject correlation as a worst-case approach, using proc Power in SAS.

μ (sd) comparator	μ (sd) active	Alpha	Power	Sample size
25 (50)	10 (15)	0.05	71.9 %	40
25 (50)	10 (15)	0.05	81.2 %	50
25 (50)	10 (15)	0.05	87.7 %	60
25 (50)	10 (15)	0.05	92.2 %	70

Taken into consideration a discontinuation of 20%, the endpoint of RV1 is sufficiently supported by randomizing at least 72 subjects.

If the number of subjects contributing to the primary analysis is less than 60 subjects, it must be carefully considered to include additional subjects (subjects replaced), to maintain sufficient power in the primary analysis.

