4.6. Total number of devices intended for the clinical investigation

Seventy-two subjects will be included in the study and have a catheterization performed in a randomized order with the investigational device or comparator, so the total use is 144 catheters.

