10.1. Level of significance and power

A significance level of alpha 0.05 (2-sided) will be applied.

The power for concluding superiority of the investigational device is at least 90% or higher.

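### Table 10-1 gives each sample size the power of twice as many subjects: under the plan's own assumptions 60 subjects give about 59% power, not 87.7% or 90%

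*Combined protocol and SAP*

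**What the plan says.** Section 10.6 (Sample size) says that the RV1 endpoint "is judged to be accommodated by 60 subjects with a power of ~ 90%, assuming a difference of 15 mL", with standard deviations of 50 mL for the comparator and 15 mL for the investigational device. The caption of Table 10-1 describes a crossover calculation, "assuming no within subject correlation as a worst-case approach, using proc Power in SAS". The table prints power of 71.9%, 81.2%, 87.7% and 92.2% for sample sizes 40, 50, 60 and 70.

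The section headed Level of significance and power (numbered 10.1 for a second time, after 10.6) sets the test, "A significance level of alpha 0.05 (2-sided) will be applied", and then states: "The power for concluding superiority of the investigational device is at least 90% or higher".

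The numbers are totals for the whole trial. Section 10.6 randomises at least 72 subjects to allow for 20% discontinuation, and asks for replacement to be considered if fewer than 60 are in the primary analysis. Section 4.6 says that 72 subjects "have a catheterization performed in a randomized order with the investigational device or comparator, so the total use is 144 catheters", that is, one catheterisation per device per subject.

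**The concern.** With zero correlation, a crossover gains nothing from pairing beyond using each subject twice, so the variance of the within-subject difference is the full sum of the two variances. A 15 mL difference against a standard deviation of about 52 mL is a standardised effect of about 0.29, and 60 pairs are too few for 90% power at that effect size.

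RV1 superiority is the only pass/fail criterion (section headed Pass/fail criteria). The same table supports the target of 60 evaluable subjects, the 72 randomised and the replacement trigger. If the table is wrong, the sponsor, the ethics committees and the regulators have accepted a much higher risk of an inconclusive trial than the plan tells them. A non-significant result would also be weighed as if it came from a trial with 90% power.

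**Working it through.** **Inputs, all from the plan**

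- Means 25 and 10 mL, difference 15 mL; SDs 50 and 15 mL (section 10.6, Table 10-1)
- Within-subject correlation r = 0 (Table 10-1 caption)
- Two-sided alpha 0.05 (Level of significance and power)
- One measurement per device per subject (section 4.6)

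**Formulae**

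- SD of the paired difference = sqrt(50² + 15² − 2·r·50·15). At r = 0 this is sqrt(2725) = 52.20 mL.
- Noncentrality = 15 / (52.20/√n), with n − 1 degrees of freedom. Power comes from the noncentral t distribution.
- For n = 60: standard error 52.20/√60 = 6.74 mL, noncentrality 15/6.74 = 2.23, critical value 2.00, power 59.1%.

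**Trying to reproduce the plan's figures**

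| Listed N | Power printed in Table 10-1 | Power with N pairs | Power with 2N pairs |
|---|---|---|---|
| 40 | 71.9% | 42.6% | 71.86% |
| 50 | 81.2% | 51.3% | 81.21% |
| 60 | 87.7% | 59.1% | 87.74% |
| 70 | 92.2% | 65.9% | 92.17% |

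With N pairs no row is reproduced. With 2N pairs every row agrees to the printed decimal.

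**Other readings at N = 60**

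- One-sided test: 71.1%, and the plan specifies two-sided.
- Normal approximation instead of t: 60.5%.
- Two independent groups of 60, unequal variances: 59.3%.
- Positive correlation: the r needed to give the printed power is 0.932, 0.926, 0.922 and 0.922 for the four rows. These values contradict the caption, and no single one fits the table.
- Root-mean-square SD, sqrt(2725/2) = 36.9 mL, used as the SD of the difference with N − 1 degrees of freedom: 87.2%, close but not equal to the printed figure. With 2N − 1 degrees of freedom it gives 87.74%, because halving the variance is algebraically the same as doubling n.
- The planned mixed model (section 10.3): in complete, balanced data the device contrast has essentially the same standard error, so the model adds no power.

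**What the design delivers at r = 0**

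- 60 evaluable: 59.1%, so the type II error is 40.9%. The table's own row implies 100 − 87.7 = 12.3%.
- All 72 evaluable: 67.2%.
- 72 less the plan's 20% loss: 72 × 0.8 = 57.6. With 57 evaluable, power is 56.8%.
- Needed for 90%: 130 evaluable, or 130/0.8 = 162.5, so 163 randomised. Needed for 80%: 97 evaluable.
- Difference detectable with 90% power: 22.2 mL at 60 subjects and 20.2 mL at 72.

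**Sensitivity to correlation (an assumption; the plan gives only zero)**

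| r | Power, 60 subjects | Power, 72 subjects |
|---|---|---|
| 0 | 59.1% | 67.2% |
| 0.25 | 65.5% | 73.6% |
| 0.5 | 73.0% | 80.7% |
| 0.75 | 81.5% | 88.1% |
| 1.0 | 90.4% | 94.8% |

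For 90% at 60 subjects, r must be about 0.99.

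**The case against.** The strongest objection is that zero correlation is labelled a worst case. The true correlation may be positive, so 59% is a planned lower figure and not the known power of the trial. That stands, and every power figure here is conditional on it. It does not rescue the plan. The printed powers are attached to the zero-correlation case, and 90% with 60 subjects would need almost perfect correlation.

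Second, the SAS code is not shown, so the cause of the doubling is inferred. The software may have returned a number per sequence that was then read as a total, catheterisations may have been counted as pairs, or the variance of the difference may have been halved. If the output was per sequence, the powers are right and the column label is wrong. That also stands, and it affects how the table should be repaired. It does not change the power of a trial with 60 subjects in total.

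Third, the claim of at least 90% names no sample size. On the table's own terms it could refer to the 72 randomised, because the row for 70 prints 92.2%. The gap between 87.7% and 90% is therefore only a secondary inconsistency.

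Fourth, RV1 cannot be negative and both assumed SDs exceed their means, so a normal-theory calculation is approximate. If gamma distributions with the same means and SDs are assumed (the plan names no distribution), simulated power at 60 subjects is about 67%. That is still far below 87.7%.

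Finally, the error leaves the type I error, the estimator and the decision rule untouched, and a positive result would stand. This is correct and limits the consequence to the power claim and the numbers built on it.

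**Conclusion.** The concern holds. Under the plan's stated difference, SDs, zero correlation and two-sided 5% level, 60 evaluable subjects give 59.1% power, which is 87.7 − 59.1 = 28.6 percentage points below the table. The printed powers correspond to 120 pairs at that row and to twice the listed number in every row. Neither the roughly 90% in section 10.6 nor the at-least-90% claim is met at 60 subjects or, with zero correlation, at 72 (67.2%). The exact match across four rows makes a doubling error by far the most likely explanation, but how it arose is not documented and the conclusion does not depend on it. This must be corrected, because the trial's size and its replacement rule rest on this table.

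**What to change.** 1. Check the SAS run behind Table 10-1. Then either correct the powers to 42.6%, 51.3%, 59.1% and 65.9% for 40, 50, 60 and 70 subjects, or relabel the sample-size column so that it shows the number of subjects the powers belong to (80, 100, 120 and 140). Reconcile the result with the totals of 60 and 72.
2. Restate section 10.6 and the section on level of significance and power as about 59% power with 60 evaluable subjects and 67% with 72 under zero correlation, or as 90% power for a difference of about 22 mL with 60.
3. If CP322, CP323 and CP324 support a positive within-subject correlation, state the estimate and its source, show power over a range of values, and remove the zero-correlation label from the caption.
4. Revisit the justification for the 60-subject replacement trigger, which currently relies on the incorrect row.

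The cost is one rerun of a power calculation and a wording amendment. The stated power becomes less favourable. Correcting the statement needs no added subjects. Whether to enlarge the trial (130 evaluable for 90% power at zero correlation) is a separate decision that the sponsor can then take on correct figures.

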10.2. Definition of analysis populations

Screening Failures (SF), Intention to Treat (ITT), Full Analysis Set (FAS), Safety and Per Protocol (PP) analysis set will be defined at a formal data review meeting prior to database lock. As a minimum, the data manager, the clinical manager, and the statistician will be involved in the classification of subjects.

Subjects not adhering to inclusion and/or exclusion criteria are considered screening failures (SF) and are not included and hence not randomised.

- The Safety population will constitute all subjects included i.e., subjects who have given informed consent and fulfils the in- and exclusion criteria.
- The ITT population will constitute all randomised subjects.
- The full analysis set is a modified ITT population i.e., a sub-population of the ITT population, and will constitute all randomised subjects, who have been exposed to at least one device, with at least one endpoint recorded (data non-missing).
- The PP is a sub-population of the full analysis set where all subjects have received treatment as per protocol.

Individual endpoints/data points may be excluded from the analysis, even though the corresponding subject belongs to any of the pre-defined populations. Exclusion of subjects or data points must be documented.

All statistical analysis and test of hypothesis will be based on the full analysis set, and in addition, the primary endpoint will also be analysed in the PP population, whereas adverse events and device deficiencies will be assessed in the safety population.

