10.3. Analysis of the primary endpoints

Residual volume at first flow-stop, will be analysed in a linear mixed model (LMM) with subject included as a random component. Evidence of superior effect will be concluded, if the 95% confidence interval of the difference between comparator and investigational device, do not include zero.

The model will include following fixed effects.

- Visit (Visit 1 and 2 of catheterisation)
- Device (comparator and investigational device)

The primary endpoint will be evaluated with the null hypothesis being rejected at a 5% significance level (alpha 0.05).

Analysis of sensitivity

- The primary analysis will furthermore be analysed in the PP population, where subjects have received treatment as per protocol.

- Also, a Wilcoxon signed rank test will be applied the primary analysis, under the assumption of data not being normally distributed.

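### 72 randomised leaves 57.6 completers, not 60, after the plan's 20% loss, and Table 10-1 shows 87.7% power at 60 where the text claims at least 90%

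*Combined protocol and SAP*

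**What the plan says.** Section 10.6 says 60 subjects give roughly 90% power for residual volume at first flow-stop. The inputs are a 15 mL difference (25 against 10), SDs of 50 mL (comparator) and 15 mL (investigational device), and the calculation is described as "assuming no within subject correlation as a worst-case approach". Table 10-1 lists 71.9%, 81.2%, 87.7% and 92.2% power at 40, 50, 60 and 70 subjects.

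The section then allows for loss: "Taken into consideration a discontinuation of 20%, the endpoint of RV1 is sufficiently supported by randomizing at least 72 subjects". It adds a safeguard: "If the number of subjects contributing to the primary analysis is less than 60 subjects, it must be carefully considered to include additional subjects". Section 6.3 says withdrawn randomised subjects can be replaced, after discussion with the sponsor.

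The section headed Level of significance and power (the second one numbered 10.1) says "A significance level of alpha 0.05 (2-sided) will be applied" and "The power for concluding superiority of the investigational device is at least 90% or higher".

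Section 4.6 makes clear that 72 is the total number of subjects, each catheterised once with each device, "so the total use is 144 catheters".

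**The concern.** There are two separate inconsistencies. First, the dropout allowance multiplies the target by 1.20 instead of dividing it by 0.80, so the randomised number does not deliver the evaluable number at the plan's own loss rate. Second, the text guarantees a power that the plan's own table does not show at that evaluable number.

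One primary endpoint decides pass or fail, so the stated power is the reader's measure of the risk that the trial misses a real effect. If it is overstated, an inconclusive result is more likely than the plan says. The safeguard is also hard to apply as written: it counts subjects contributing to the primary analysis, and a subject with data from Visit 1 only may or may not be one of those.

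**Working it through.** **Inputs.** From section 10.6: difference 15 mL, SDs 50 and 15 mL, no within-subject correlation, 60 evaluable, 20% discontinuation, 72 randomised. From the section on level of significance and power: two-sided alpha 0.05. From section 4.6: 72 is total subjects, with one paired comparison each.

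**1. Dropout**
- Reproducing the plan's figure: 60 × 1.20 = 72.
- Expected completers: 72 × (1 − 0.20) = 57.6.
- Number needed to keep 60: 60/(1 − 0.20) = 75.
- Largest loss at which 72 still leaves 60: 12/72 = 16.7%.

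With independent 20% loss, completers follow Binomial(72, 0.80), and the probability of fewer than 60 is 70%. With 75 randomised it is 43%.

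The 70% is the chance of triggering the under-60 clause only if discontinuers supply no Visit 1 data. The documents do not give the fraction who do, so I assume two values:
- A quarter of discontinuers contribute: 0.80 + 0.20 × 0.25 = 0.85, and the chance is 28%.
- Half contribute: 0.80 + 0.20 × 0.50 = 0.90, and the chance is 2.5%.

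**2. Power as printed**

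Table 10-1 gives 87.7% at 60, which is 90 − 87.7 = 2.3 points below the claimed minimum.

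**3. Power from the stated inputs**

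With zero correlation, the SD of the paired difference is √(50² + 15²) = 52.2 mL. Power comes from the noncentral t distribution with noncentrality (15/52.2) × √n and n − 1 degrees of freedom, at two-sided 0.05.

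| Subjects in Table 10-1 | Printed power | Paired t-test, that many pairs | Paired t-test, twice as many pairs |
|---|---|---|---|
| 40 | 71.9% | 42.6% | 71.9% |
| 50 | 81.2% | 51.3% | 81.2% |
| 60 | 87.7% | 59.1% | 87.7% |
| 70 | 92.2% | 65.9% | 92.2% |

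All four rows match at 80, 100, 120 and 140 pairs, and none at the printed number. Two alternatives come close at 60 without matching: a correlation of 0.9 (86.9%), or the averaged SD √((50² + 15²)/2) = 36.9 mL used as the SD of the difference (87.2%). Both conflict with the stated zero correlation. The documents do not say why the table comes out as it does.

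**4. Power at the completers 72 would leave**

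The table scale here means twice the printed number of pairs, inferred from the match above.

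| Completers | Table scale | Stated inputs |
|---|---|---|
| 57 | 86.0% | 56.8% |
| 58 | 86.6% | 57.6% |
| 60 | 87.7% | 59.1% |

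**5. What 90% would take**
- Table scale: 64 completers give 89.7% and 65 give 90.2%. With 20% loss, 65/0.80 = 81.25, so 82 randomised.
- Stated inputs: 130 completers. With 20% loss, 130/0.80 = 162.5, so 163 randomised.

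**The case against.** The best defence is that the plan already allows for the shortfall. The 72 is a minimum, withdrawn subjects can be replaced, and adding subjects must be considered below 60. The power sentence names no sample size: the table prints 92.2% at 70, and on its scale 72 analysed subjects would give 92.9%. The plan prints 87.7% openly and calls the power at 60 approximate. The dropout slip moves power by only one to two points.

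Some of this stands. The slip is small, and the plan never states in so many words how many completers it expects from 72. That 60 is the intended number is an inference, though a natural one, from the target and the under-60 clause. It is also true that the primary endpoint "will be analysed in a linear mixed model (LMM) with subject included as a random component" on the full analysis set, so a subject with one visit can contribute, and the chance of triggering the clause could be far below 70%.

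The rest does not remove the error. Replacement and top-up are discretionary, and the trigger is 60, where the table itself is below 90%. Reading the power claim at 72 analysed subjects sets aside the plan's own 20% loss.

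**Conclusion.** The concern holds. At 20% loss, 72 randomised subjects give an expected 57.6 completers against a target of 60, and 75 would be needed. Separately, the claim of at least 90% power is contradicted by the 87.7% printed at 60. Both conclusions use the plan's figures alone and need no outside assumption.

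The dropout slip by itself is minor. The larger number is the gap between the table and its inputs: 59.1% recomputed against 87.7% printed at 60, and about 57% at 57 to 58 completers. That gap assumes one paired difference per subject, zero correlation and a two-sided paired t-test, as the plan describes. A high positive correlation would narrow it, but the plan does not assume one. The table-scale figures for other sample sizes rest on an inferred method and should not be adopted as targets until the calculation has been checked.

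**What to change.** First, rerun the Table 10-1 calculation from its stated inputs. State whether the sample size column is total subjects or subjects per sequence, and give the correlation and the code. Then:

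1. In section 10.6, replace the discontinuation sentence with wording such as: 72 randomised subjects give 60 completers at up to 16.7% discontinuation, or 57 to 58 at 20%.
2. In the section on level of significance and power, replace the 90% claim with the recomputed power at that number of completers. Do not carry over 86–87% unless the rerun confirms it.
3. In the under-60 clause, say whether 60 means subjects completing both visits or any subject with data in the primary model.

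This costs a text amendment and one rerun, and the stated figures become less favourable.

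If the sponsor prefers 75, change 72 in the synopsis and in sections 4.6, 6 and 10.6. By section 4.6's count of two per subject, the catheter total becomes 75 × 2 = 150, which is three more subjects and six more catheters. That count leaves out the extra self-catheterisation at Danish sites, so it should be checked at the same time. Also, 72 fills nine randomisation blocks of 8 and 75 does not fill whole blocks. The power sentence would still need correcting, because 75 randomised leaves 60 after 20% loss, and 60 does not give 90% on either calculation.

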10.1. Level of significance and power

A significance level of alpha 0.05 (2-sided) will be applied.

The power for concluding superiority of the investigational device is at least 90% or higher.

10.2. Pass/fail criteria

To demonstrate superiority of the investigational device, the null hypothesis of the primary endpoint must be rejected, at a 5% significance (alpha 0.05).

11. Data management

Data management and the final statistical analyses of all measurements described in this protocol are carried out by the Clinical Strategies team, Coloplast A/S.

Data will be collected through an electronic data capturing (EDC) system on electronic Case Report Form (eCRF), a secure, internet-based case report form. This system will be used to record all subject information collected in the investigation for secure data tracking and centralised data monitoring ("remote monitoring") done by monitors, as defined in the monitoring section.

The EDC system used is Rave EDC, version 2022.3.0, delivered by Medidata Solutions Inc. The system is designed to be compliant with the FDA requirements of 21 CFR part 11. It is a validated data management system allowing only qualified and trained personnel to enter the system. The system has full audit trail and electronic signature.

The data management system has restricted role-based access control. The principal investigator or delegate an CRA must be trained in the system prior to getting access. The sponsor will be responsible for training the principal investigator or delegate, in completion of the eCRF. The training is web-based and must be completed before access to the investigation is granted. Training will be documented in the data management system. The data manager will also demonstrate the system on a virtual meeting. Only the principal investigator, or delegate, will be authorised to enter data in the eCRF.

The monitor, using his/her personal login information shall verify all critical data points against the source documents and issue electronic queries for the authorised clinical site personnel to respond, as defined in the monitoring section.

A critical quality control will be performed by the sponsor's data management team and queries issued where needed. Such queries must be resolved by the site personnel.

The principal investigator, using his/her personal login information, shall sign each eCRF before the database can be locked. This must be done after approval from the data management team.

Automated, real-time access to the data enable control on study compliance and safety assessments.

A full audit trail ensures, that each user's (site personnel, monitor, sponsor, data manager) access to and actions in the system is tracked.

The Data Validation Plan describes which edit checks, range checks, and other consistence checks that will be done on the clinical data during conduct of the investigation. The Data Validation Plan will be developed in collaboration with the Clinical Manager and the Statistician and will be aligned with the monitoring section.

Principal Investigator, or delegate, at the clinical site will perform primary data collection directly into the eCRF or drawn from source-document (i.e., medical records or notes) reviews. The eCRF will be completed on a continuous basis starting from the point of enrolling the subject to final follow up.

The eCRF will be completed by the principal investigator, or delegate, who have signed the Site Personnel Signature and Delegation List and Clinical Investigation Training Log. It will be the responsibility of the principal investigator to ensure that all measurements and observations are correctly noted in the eCRF.

All assessments and observations throughout the investigation for each subject must be carefully recorded in an eCRF during the visit or immediately after. The eCRF makes it possible to enter data right away when they are obtained. This is the preferred way of collecting data. In case this is not possible the data should be entered no later than 7 days after the visit / procedure. This deadline will be shorter after LPO at the site, and will be agreed with the monitor.

In the unforeseen situation, where site cannot establish connection to the EDC system, a paper CRF (pCRF) has been printed and supplied by sponsor.

